4.5. Study Day and Study Week

Study days will be numbered relative to the earliest date an ABS eMDPI device was dispensed (ie, ... -2, -1, 1, 2, ...). Day 1 is defined as the earliest date an ABS eMDPI device was dispensed and Day -1 is the day before the first ABS eMDPI device was dispensed.

Week I is defined as study day $(j + 1)$ to study day $(j + 7)$, inclusive where $I = 1$ to 12 and $j = 0, 7, 14, 21, 28, 35, 42, 49, 56, 63, 70, 77, 84$, respectively.

4.6. Handling Withdrawals and Missing Data

Any data that was collected prior a patient's withdrawal from the study will be used for analysis and presented in the data listings.

The following imputation rules will be used;

- If the return date of the last ABS eMDPI device returned is missing the patient's last date of contact if the patient withdrew from the study or the patient's study completion date will be used as the return date (see Section 4.4 and Section 10.2).
- Adverse events or serious adverse events with missing start dates will be considered treatment emergent (see Section 10.4).
- If a patient never used the ABS eMDPI during the study or download of a given ABS eMDPI device was not successful, study day and weekly inhalational flow values will be missing. If download of a given wrist or ankle accelerometer was not successful, TDS and SDI indices will be missing. These missing data will not be imputed.
- In the derivation of Study Day X Inhalation flow values, if there was no albuterol use on Study Day X , then the closest preceding nonmissing Study Day Inhalation is used as the 'Study Day X Inhalation' and the inhalational flow values for Study Day X are assigned accordingly (see Section 7.2.1).
- For patients in the ankle accelerometry analysis set, if no step data are available for study day 1 through study day 7, the 'baseline TDS' is the first available TDS after study day 7 (see Section 4.2.4).
- For patients in the wrist accelerometry analysis set, if no sleep parameter data are available for study day 1 through study day 7, the 'baseline value of a given sleep parameter' is the first available valid sleep parameter value after study day 7 (see Section 4.2.5).
- In the derivation of Study Day X TDS if TDS are missing on Study Day X , then the average of the nonmissing TDS of the 7 days preceding Study Day X is computed and assigned to Study Day X TDS (see Section 7.3.1).
- In the derivation of Study Day X nighttime average sleep latency time if nighttime average sleep latency time is missing on Study Day X , then the average of the nonmissing nighttime average sleep latency time of the 7 days preceding Study Day X is computed and assigned to Study Day X (see Section 7.4.1).
- In the derivation of Study Day X longest nighttime wake episode if longest nighttime wake episode is missing on Study Day X , then the greatest nonmissing longest nighttime wake episode of the 7 days preceding Study Day X is computed and assigned to Study Day X (see Section 7.4.1).
- In the derivation of Study Day X total time awake at night if total time awake at night is missing on Study Day X , then the average of the nonmissing total time awake at night of the 7 days preceding Study Day X is computed and assigned to Study Day X (see Section 7.4.1).

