9.3. Data Handling Conventions

For all variables, only the observed data from the patients will be used in the statistical analyses, that is, there is no plan to estimate (impute) missing data, unless otherwise specified in the analysis plan.

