7.2. Inhalational Flow Values

7.2.1. Inhalational Flow Values Definitions

Study Day X and Week Y inhalational flow values are defined as follows:

Study Day X Inhalational Flow Values: The inhalational flow values for study day X are computed using the set of inhalations taken by the patient on study day X . Among these inhalations, the inhalation with the highest maximal MIF value is considered the 'Study Day X Inhalation'. The Study Day X MIF, inhalational volume, inhalation duration, and time to MIF values are those of the identified 'Study Day X Inhalation'. If there was no albuterol use on Study Day X , then the closest preceding nonmissing Study Day Inhalation' is used as the 'Study Day X Inhalation' and the inhalational flow values for Study Day X are assigned accordingly.

Week Y Inhalational Flow Values: The inhalational flow values for Week Y are computed using the set of inhalations taken by the patient during a given week on the study. Among these inhalations, the inhalation with the highest MIF value is considered the 'Weekly Y Inhalation'.

The Weekly Y MIF, inhalational volume, inhalation duration, and time to MIF values are those of the identified ‘Weekly Y Inhalation’.

Note, if a patient never used the ABS eMDPI during the study or download of a given ABS eMDPI device was not successful, study day and weekly inhalational flow values will be missing.

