7.5.2.1. Within Patient CE-COPD Analyses

For each CE-COPD event occurring at least 2 weeks after baseline, device-use measures (albuterol use, inhalational flow [MIF], inhalational volume, and time to MIF) will be summarized for each of 2 weeks of interest: first- 'CE-COPD-adjacent week', the week immediately preceding the onset of CE-COPD symptom (ie, day 1 through 7 preceding the date of the CE-COPD symptom onset), and second – 'CE-COPD-Prior Adjacent week', the week preceding that week (ie, during day 8 through 14 preceding the date of the CE-COPD symptom onset). Summary measures of daily and or weekly use will be compared between the two weeks, as proposed below:

Albuterol use measures:

- total number of inhalations in that week
- the maximal daily number of inhalations in that week
- the mean number of daily inhalations (ie, total number of inhalations divided by number of days with number>0)
- occurrence of a single day's albuterol use exceeding 4 inhalations
- occurrence of a single day's albuterol use exceeding 8 inhalations
- occurrence of a single day's albuterol use exceeding 12 inhalations
- number of days when albuterol use exceeding 4 inhalations
- number of days when albuterol use exceeding 8 inhalations
- number of days when albuterol use exceeding 12 inhalations

To note, in this analysis, no inhalation in any day will be taken as a 0 count.

Inhalation flow values parameters:

- maximal daily MIF during the week
- minimal daily time to MIF within a week
- maximal total daily inhalational volume within a week

To note, if no inhalation was taken at a specific day, flow value parameters will be missing and will not be imputed.

Analysis will be based on all patients CE-COPDs for which there are 14 days (or more) prior to the CE-COPD onset, where patient has been on study and CE-COPD free.

Descriptive statistics of use measures in the 'CE-COPD-adjacent week' and 'CE-COPD-Prior Adjacent week' will be presented.

Continuous measures will be compared between the 2 weeks using paired t-test (and Wilcoxon Signed Ranks test) whereas binary patterns will be compared using Mc-Nemar test.

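### Filling single study days from earlier days biases the pre-peak tables: flow, steps, sleep latency and time awake are attenuated, and longest wake episode is inflated

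*SAP*

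**What the plan says.** SAP 4.6, repeated in 7.2.1, 7.3.1 and 7.4.1, gives three fill rules for single study days:

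- **Flow.** If there was no albuterol use on the day, "then the closest preceding nonmissing Study Day Inhalation is used", and "the inhalational flow values for Study Day X are assigned accordingly". No limit is set on how old that inhalation may be.
- **Steps, sleep latency and total time awake.** For a missing step count, "then the average of the nonmissing TDS of the 7 days preceding Study Day X is computed and assigned to Study Day X TDS". The two sleep measures have the same form. No minimum number of observed days is required.
- **Longest nighttime wake episode.** If missing, "then the greatest nonmissing longest nighttime wake episode of the 7 days preceding Study Day X is computed and assigned to Study Day X".

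The resulting day values are tabulated, actual and as change from baseline, at 1, 3, 5, 7, 10, 14 and 21 days before the symptom peak (SAP 7.2.2.1, 7.3.2.1, 7.4.2.1).

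Elsewhere the plan differs. In the within-patient two-week comparison, a day without inhalation means that "flow value parameters will be missing and will not be imputed" (SAP 7.5.2.1). Protocol 9.3 says "there is no plan to estimate (impute) missing data", but excepts whatever the analysis plan specifies. Patients who never used the inhaler and failed downloads stay missing (SAP 4.6). SAP 8 plans no sensitivity analysis.

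**The concern.** The study asks what happens in the days just before an exacerbation. A fill built only from earlier days replaces late information with early information exactly where the tables look for change. If the carried flow value happens to be the baseline inhalation (the highest-MIF inhalation of week 1, SAP 4.2.3), the change from baseline is 0 by construction.

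The wake-episode rule has the opposite fault. Its baseline is an average over days 1 to 7 (SAP 4.2.5), but a missing night receives a maximum over 7 nights, so a filled night tends to show a rise when nothing has changed. The Study Day X SDI composite, being a sum, inherits this by definition, although 7.4.2.1 tabulates only the three components by day.

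A day without use is also not a lost measurement: no inhalation took place, so there is no flow value to recover. SAP 7.5.2.1 treats it that way and 7.2.1 does not. The plan does not ask for a count of filled values, so a reader of the tables could not tell how much of a day's mean was carried from earlier days.

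**Working it through.** **The plan's own figure.** The documents give none for missing or no-use days. The event count (SAP 2.3) does reproduce: 360 × 1.095 × 12/52 = 90.97, where 1.095 is the mean of 1.05 and 1.14. The Poisson 2.5% and 97.5% points are 73 and 110. At the same rate and dropout, one accelerometer subset of 100 gives 100 × 0.9 × 1.095 × 12/52 = 22.7 events, of which 0.14 × 22.7 = 3.2 are severe. A few filled days can therefore move a TDS or SDI day mean.

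**Assumed change.** A true change builds linearly over L days: at k days before the peak, its share of the day -1 change is f(k) = max(0, (L + 1 − k)/L). The ramp lengths, filled shares and puff rates below are all assumptions.

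**7-day-mean fill on day -1.** A filled day shows the mean of f(2) to f(8). For L = 7 this is (6+5+4+3+2+1+0)/7 ÷ 7 = 3/7 = 43%. If a share m of patients is filled, the mean change is understated by m × (1 − share shown).

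| L (days) | Share shown on a filled day | m = 10% | m = 20% | m = 30% |
|---|---|---|---|---|
| 3 | 14% | 9% | 17% | 26% |
| 7 | 43% | 6% | 11% | 17% |
| 14 | 71% | 3% | 6% | 9% |

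A change confined to day -1 is lost completely on filled days, so the understatement then equals m.

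**Flow carry-forward on day -1.** Take use as Poisson (the form SAP 7.1.2.3 uses for puffs) at a constant λ per day, so the probability of a no-use day is q = exp(−λ). The value shown comes from the most recent day with use, and the expected loss is (q + q² + … + q^L)/L.

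| λ (puffs/day) | No-use days | Loss, L = 7 | Loss, L = 3 |
|---|---|---|---|
| 0.5 | 61% | 21% | 40% |
| 1 | 37% | 8% | 18% |
| 2 | 14% | 2% | 5% |
| 4 | 2% | under 1% | under 1% |

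If use rises by 1 puff/day by the day before the peak, the loss at λ = 1 falls to 2% (L = 7) or 6% (L = 3). The missing look-back limit matters at low use: at λ = 0.5, q⁴ = 0.135, so about 14% of all days would carry a value at least 4 days old.

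**7-night-maximum fill.** With no true change and normal, independent nights, the expected maximum of 7 nights is 1.35 within-patient SD above the mean (simulated). The spurious rise in the day mean is m × 1.35: 0.14, 0.27 and 0.41 SD at m = 10%, 20% and 30%. With a true day -1 rise of 1 SD and L = 7, a filled night averages 1.84 SD; at m = 20% the day mean is 0.8 × 1 + 0.2 × 1.84 = 1.17 SD.

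**The case against.** The strongest reply is about scope.

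- **Primary predictor.** No day-level fill rule is listed for albuterol counts. The hypothesis test in 7.1.2.3 uses puff counts, and 7.5.2.1 counts a no-use day as 0.
- **Other unfilled analyses.** The paired two-week flow comparison does not impute. Weekly steps, latency and time awake divide by non-missing days.
- **What is left.** The rules reach descriptive tables of secondary predictors in an exploratory study.
- **Flow.** Patients must be current SABA users. The worked example in 7.1.1 is 28 inhalations in 7 days, or 4 per day, where the loss is negligible. If use rises before an event, as hypothesised, no-use days become fewer near the peak.

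All of that stands and limits the point.

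Two stronger readings are tempting. A reader might infer that the rules hide or erase the pre-exacerbation change. They do not: under the 7-day ramp a filled day still shows 43% of it, and unfilled days show all of it. A reader might also infer that the SAP breaches the protocol. It does not, because Protocol 9.3 allows imputation that the SAP specifies, and the SAP does specify it. Nor do the rules clearly understate variability for flow, since a carried value is another single-day value from the same patient.

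Observed-only tables are not a full cure either. Flow means would come from whichever patients used the inhaler that day, and accelerometer days lost because the patient was worsening would still bias the result.

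This does not rescue the rules. The maximum fill has no counterpart in the baseline it is compared with, and the two opposite treatments of a no-use day are not explained in SAP 20.

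**Conclusion.** The point holds for the day-level pre-peak tables of flow, TDS and SDI, and no further. Carry-forward and mean filling pull late values toward earlier ones. The day -1 change in mean-filled measures is understated by about 6% to 17% for a 7-day ramp, with 3% to 26% as the span across ramps of 14 and 3 days, all at 10% to 30% filled. Flow loss is material only at low use. The maximum rule is the clearest fault, because it produces an apparent rise in longest wake episode without any true change.

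These sizes depend on filled shares, ramp shapes and puff rates that the documents do not give; the directions do not depend on the exact values, provided that the change builds toward the peak. The documents do not support extending the point to the albuterol hypothesis test, the paired two-week comparison or weekly TDS. The change is worth making because it is cheap and the bias is built in.

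**What to change.** Drop the 7-night-maximum rule from SAP 4.6 and 7.4.1. Base the tables in 7.2.2.1, 7.3.2.1 and 7.4.2.1 on observed values only, with the number contributing at each day, and amend 4.6, 7.2.1, 7.3.1 and 7.4.1 to match. This also brings the treatment of no-use flow days into line with 7.5.2.1. If the sponsor keeps carry-forward or mean filling, show it only as a secondary table, with the count of filled values at each time point.

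The cost is SAP wording, made before database lock, and somewhat less programming. The downside is fewer values per day, which matters most in the accelerometer subsets with about 23 expected events each. The contributing patients will also differ between days, and bias from days missing because of worsening will remain; the table notes should say so.

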5. STUDY POPULATION

5.1. General

The ITT analysis set will be used for all study population summaries unless otherwise specified. The data will be listed for all patients entered into the database.

5.2. Patient Disposition

Data from patients screened; patients who were screen failures; patients who re-screened; patients screened but not enrolled and reason for non-enrollment; patients who are enrolled; patients enrolled but who do not use ABS eMDPI at least once; patients in the ITT analysis set; patients in the ankle accelerometry cohort and patients in the wrist accelerometry cohort; patients who complete the study; and patients who withdraw from the study and the reason for withdrawal will be summarized using descriptive summary statistics (n, %) for all patients entered into the database.

5.3. Demographics and Baseline Characteristics

Patient demographic and baseline characteristics will be summarized for all patients in the ITT analysis set using descriptive statistics. Demographic and baseline characteristics will include: age, sex, race, ethnicity, weight, height, and body mass index (BMI), vital signs, TDS, inhalational flow values and SDIs.

The formula for BMI is: $BMI = \frac{\text{weight}}{\text{height}^2}$,

where weight is in kilograms (kg), height in meters (m) and BMI is kg/m².

Baseline inhalational flow values include MIF, inhalational volume, inhalation duration, and time to MIF. Baseline SDIs include nighttime average total time in bed, nighttime average total sleep time, nighttime average sleep latency time, nighttime average wakening after sleep onset, total time awake at night, daytime average minutes asleep, longest daytime sleep episode and longest nighttime wake episode.

Demographics and baseline characteristics will be summarized by analysis set (ITT analysis set and the ankle and wrist accelerometry analysis sets).

5.4. Medical History

All medical history will be coded using the most current version of the Medical Dictionary for Regulatory Activities (MedDRA) at the time of database lock. The incidence of medical history abnormalities will be summarized using descriptive statistics by system organ class (SOC) and preferred term (PT). Patients are counted only once in each PT and SOC category even if they have multiple applicable findings.

Summaries will be provided for the ITT analysis set and the ankle and wrist accelerometry analysis sets.

5.5. COPD History

Patients' COPD history data will be summarized. This will include duration of COPD.

Summaries will be provided for the ITT analysis set and the ankle and wrist accelerometry analysis sets.

5.6. Clinical COPD Exacerbations History

Patients' COPD exacerbations history data will be summarized. This will include COPD exacerbations in the past 12 months or previous year, hospitalizations, emergency room visits, urgent care, doctor visits for COPD exacerbations, ICU admissions, and systemic steroids administration for COPD.

Summaries will be provided for the ITT analysis set and the ankle and wrist accelerometry analysis sets.

5.7. Prior Therapy and Medication

All prior medications will be coded using the most current version of the World Health Organization drug dictionary (WHO Drug) at the time of database lock. The incidence of prior medications will be summarized using descriptive statistics (count and percentages) by therapeutic class and PT term. In addition, a summary table of the incidence of prior COPD medications will be provided. Patients are counted only once in each therapeutic class category, and only once in each PT term category. Prior medications will include medications taken within 30 days prior to the first day that IMP is dispensed.

Summaries will be provided for the ITT analysis set and the ankle and wrist accelerometry analysis sets.

5.8. Childbearing Potential and Methods of Contraception

Information related to childbearing potential, contraception, and menopause will be collected at Screening and at the Final/Early Termination visit. All information for childbearing potential will be provided in a listing by patient.

5.9. Study Protocol Violations

Any deviation from the protocol that affects, to a significant degree, (a) the safety, physical, or mental integrity of the patients in the study and/or (b) the scientific value of the study will be considered a protocol violation. Protocol violations include non-adherence on the part of the patient, the investigator, or the sponsor to protocol-specific inclusion/exclusion criteria, primary outcome measure criteria, or good clinical practice (GCP) guidelines; noncompliance to study drug administration; use of prohibited medications; or any other deviations that may have an impact on the processes put in place for the care and safety of the patients.

Protocol violations recorded in the Clinical Trial Management System during the study will be summarized overall and for each of the following categories using descriptive statistics:

- Informed Consent Procedures

- Inclusion/Exclusion Criteria
- Concomitant Medications/Therapy
- Lab Assessments/Procedures
- Study Procedures
- Serious Adverse Events
- Randomization Procedures/Dosing
- Visit Schedule/Interval

Of note, any recorded ‘Randomization Procedures/Dosing’ violations related to medication errors, overdose, misuse, abuse, off-label use and occupational exposure will be summarized in the sub-category ‘Non-compliance to study medication’.

Patients with at least 1 protocol violation will be summarized by the above categories (sub-categories) using count and percentages, by analysis set (ITT analysis set, and the ankle and wrist accelerometry analysis sets).

5.10. eMDPI Time on Study; Days and Weeks

Summary statistics of the eMDPI time on study in days and weeks (days divided by 7) will be presented overall and by CE-COPD status and by CE-COPD severity (Yes: severe, moderate; No) for the ITT analysis set, ankle accelerometry analysis set and the wrist accelerometry analysis set.

6. EFFICACY ANALYSIS

Efficacy will not be assessed in this study. Endpoint analyses are described in Section [7](#).

7. ENDPOINT ANALYSES

All endpoint analyses will be performed using the ITT analysis set.

Data listings will be presented by patient.

7.1. eMDPI: Albuterol Use

7.1.1. Albuterol Use Definition

Baseline albuterol use is defined as the mean number of inhalations per day from day 1 to day 7. If no inhalations were taken during study day 1 through study day 7, the ‘baseline inhalation’ is the first available inhalation after study day 7. For analyses relative to baseline albuterol use, patients who had a CE-COPD during study day 1 through study day 7 will be excluded.

Week 1 Patient Albuterol Use: Week 1 patient albuterol use is each patient’s total number of albuterol inhalations taken and the number of days used during the first week (study day 1 through study day 7) of study participation with an indicator of whether or not the most frequent daily usage of albuterol is in 1 of the following 3 categories: (a) 0 to 2 inhalations, (b) 3-6 inhalations and (c) > 6 inhalations. It is presented as WK1:I#iD#dMTN#n, where “i” is the number of albuterol inhalations and “d” is the number of days used in the first 7 days of the study, and “n” is an indicator of whether or not the most frequent daily usage of albuterol falls into one of the 3 categories. If there is a tie in the most frequent daily usage, the category with the highest number of inhalations will be reported. For example, “I28D7MTN2” indicates a total of 28 inhalations were taken, albuterol use was used each of the 7 days and the highest most frequent usage per day falls into category 2 with 3-6 inhalations.

Week 2 Patient Albuterol Use: Week 2 patient albuterol use is each patient’s total number of albuterol inhalations taken and the number of days used during the second week (study day 8 through study day 14) of study participation with an indicator of whether or not the most frequent daily usage of albuterol is in one of the following 3 categories: (a) 0 to 2 inhalations, (b) 3-6 inhalations and (c) > 6 inhalations. It is presented as “WK2:I#iD#dMTN#n”, where “i” is the number of albuterol inhalations and “d” is the number of days used in the second week of study, and “n” is an indicator of whether or not the most frequent daily usage of albuterol is in one of the 3 categories. If there is a tie in the most frequent daily usage, the category with the highest number of inhalations will be reported.

14-Day Patient Albuterol Use: 14-day patient albuterol use is each patient’s total number of albuterol inhalations taken and the number of days used during the first 14 days (study day 1 through study day 14) of study participation with an indicator of whether or not the most frequent daily usage of albuterol is in one of the following 3 categories: (1) 0 to 2 inhalations, (2) 3-6 inhalations and (3) > 6 inhalations. It is presented as “D14:I#iD#dMTN#n”, where “i” is the number of albuterol inhalations and “d” is the number of days used in the first 14 days of study, and “n” is an indicator of whether or not the most frequent daily usage of albuterol is in one of the 3 categories. If there is a tie in the most frequent daily usage, the category with the highest number of inhalations will be reported.

Albuterol use will be examined by the following 3 parameters; (i) total number of inhalations in the days preceding the peak of a CE-COPD, (ii) number of days prior to the peak of a CE-COPD when albuterol use increased, and (iii) number of albuterol uses in the day preceding a CE-COPD.

The maximum number of inhalations taken within a 24-hour period by each patient: The date and time stamp of the inhalations are taken into consideration when determining the maximum number of inhalations taken within a 24-hour period by each patient. For patients who experienced a CE-COPD, the maximum number of inhalations taken within a 24-hour period is determined among the days prior to the date of the symptom peak of the exacerbation.

